Increase in early onset colorectal cancer (EOCRC) has been dramatic since 2012, with a 46% increase among those under 50. Recent data indicate a strong risk factor for EOCRC is insufficient dietary intake of vitamin D, and vitamin D insufficiency among adults in the US is 42%, with those ages 20-39 with the highest prevalence. Evidence indicates that dietary and circulating vitamin D levels are regulators of immune homeostasis, in part by altering the gut microbiome. The human gut microbiome is the community of bacteria that reside within the human intestine, and their composition and function are strongly linked to CRC. Very little is known about the complex interaction of vitamin D with the microbiome over time in one individual, and its impact on markers of CRC risk. In order to produce robust analysis of these interactions, longitudinal samples with detailed dietary intake information from healthy human subjects consuming vitamin D or placebo are needed.

2 Background, Rationale, and Aims

2.1 Relationship between Dietary Intake and the Microbiome

Aim 1: To elucidate the complex relationship between the diet and microbiome using longitudinal data and mathematical modeling.

The complex relationship between dietary intake and the microbiome, and the potential health implications of human exposure to microbial metabolites, are only beginning to be understood. It is well known that altered dietary intake can trigger rapid, although transient, changes in the composition of the microbiome in as little as 1 to 2 days. The biggest factors in determining microbial response to diet are thought to include an individual's starting microbiome, long-term dietary habits, and environmental exposures. However, there is some controversy over the extent to which long-term dietary patterns (i.e. vegan v. omnivore) influence the composition of the microbiome.

We still do not have a good understanding of how small dietary differences from day-to-day impact the microbiome. Recently the application of machine learning to a large dataset of microbiome, diet, anthropometrics, and blood test data was successfully used to predict blood glucose response to variable meal compositions. This finding suggests that personalized nutrition and optimal diets for health may be feasible in the future. A longitudinal dataset with accurately recorded dietary data and multiple samples over 12 weeks will provide valuable insight into the changes that occur at the individual level over time, while controlling for dietary trends and initial microbiome composition.

2.2 Vitamin D Intervention

Aim 2: To identify shifts in the composition of the human microbiome and CRC risk factors specifically caused by the consumption of Vitamin D supplements.

IRB # 1845028-2 Version 3

Vitamin D is one of 4 fat-soluble vitamins that are only obtained from dietary or supplementary intake, and which is necessary for healthy immune function, bone metabolism and electrolyte absorption.⁸⁻¹¹ Since the 1980's intake vitamin D containing foods, milk, eggs, fish and mushrooms has been declining in the United States. 12 Most concerning has been the sharp decline in consumption of cow's milk, which is a primary source of vitamin D, particularly among young females. 13 Unfortunately, there has also been a sharp rise in EOCRC since 2000, from a rate of 5.9 cases/100,000 to 8.5 in 2018 (SEER). Projections for 2030 suggest 23% of rectal and 11% colon cancer will be diagnosed in US adults under the age of 50.14 Recently, however, a study using incident cases of EOCRC from the Nurses' Health Study II, demonstrated a 50% reduced risk of EOCRC from total dietary intake of vitamin D >/= 450 IU/day vs <300 IU/day (HR = 0.40, 95% CI, 0.26-0.93).¹⁵

Recent studies have determined the impact of habitual vitamin D intake and vitamin D supplementation on the human microbiome, and demonstrated beneficial modifications in composition. 16 Specifically, 12 weeks of weekly oral dose of 50,000 IU vitamin D₃ in 80 women increased the Bacteroides/Firmicutes ratio and increased probiotic bacteria Akkermansia and Bifidobacterium. 16 It is yet unclear mechanistically how Vitamin D alters the composition and function of the microbiome, but several lines of evidence indicate a bi-directional interaction. Indirect effects of Vitamin D on the microbiota include systemic effects through the vitamin D receptor (VDR), which is expressed not only in the proximal colon but also functions as a transcription factor in a large number of genes that control immune response. 17,18 Likewise. specific bacteria influence VDR expression in host cells. 19,20

In addition to vitamin D intake, the gut microbiome structure and function is also a significant risk factor for CRC development. Multiple studies demonstrate significant loss of diversity, and increases in pathogenic bacteria, Fusobacterium nucleatum and Bacteroides fragilis, are risk factors for CRC development and progression. Recent preliminary data using data from The Cancer Genome Atlas, demonstrated a distinct intra-tumor microbial composition in EOCRC vs late-onset, along with positive association between T regulator cells and inflammasome pathway.²¹ Thus, it is possible that the vitamin D insufficiency or deficiency may be also affecting gut microbiome structure and function negatively, increasing EOCRC risk.

Although dietary vitamin D supplementation has been used in the clinical setting for decades, the effect of supplementary vitamin D consumption on the structure of the microbiome has not been studied in humans in fine scale or with concomitant adjustment for dietary intake. Understanding the interaction of vitamin D with the microbiome in humans could lead to important advancements in the understanding of how vitamin D together with diet impacts the microbiome composition, and ultimately, risk of EOCRC. This study has the potential to lay the ground work for an adjunctive therapy to manipulate the microbiome to reduce risk of EOCRC. This proposed study is designed to evaluate the effect of vitamin D supplementation on the normal structure of the microbiome and data will not be used to diagnose, prevent, cure or treat disease.

IRB # 1845028-2 Version 3 Date: March. 3 2022

3 **Experimental Design**

Study participants will complete 16 days of active study involvement after providing informed consent on day 0, which will be conducted over a period of 12 weeks. There will be 4 in-person visits, including the consent visit where the participants will have contact with the researchers. Visit 1 will be the consent visit and participants who consent will receive training on how to collect stool samples, take supplements and dietary record keeping with an online diet record tool called ASA24. Visit 1 will include a fasting blood draw and body composition measurement. At visit 1 participants will receive stool collection kits for week 1 and their supply of dietary intervention supplements (gummies) as well as written instruction on how many gummies to take each day during the intervention period. They will also complete a food frequency questionnaire, the DHQIII online. At visit 2 participants will receive collection kits for week 2 and their supply of dietary intervention gummies as well as written instruction on how many gummies to take each day during the intervention period. At study visit 3, participants will complete a fasting blood draw, stool kit for Study day 16, and intervention gummies. At visit 4, this will conclude the study. Participants will complete a fasting blood draw, body composition measurement, dietary recall and mental health survey. The process for returning fecal samples is described below in Section 6.2.

3.1 **Study Outline**

Study Day 0 (Study Visit 1)

- Fasted blood draw
- Body composition
- DHQIII online
- Stool history
- Mental health questionnaires

Study Days 1-14

- Consume vitamin D or placebo as gummies for 14 days
- Consume normal diet and keep detailed dietary records using ASA24 (daily 24-hour recalls)
- Collect 1 stool sample per day for 14 days
- Study Visit 2/Study day 7 delivery of 2nd week of stool collection kits

Study Day 15 (Study Visit 3)

- Fasted blood draw
- Provide vitamin D or placebo gummies to last through week 9
- Stool history
- Post self-perceived stress scale

Study Day 16 (Study Visit 4)

- Provide remainder vitamin D or placebo gummies to last through week 12
- Provide stool collection kit for Study day 16

IRB # 1845028-2

Study Day 16 (Study Visit 5)

- · Fasted blood draw
- Stool history
- ASA24 dietary record
- Body composition
- Collect final stool sample
- Post self-perceived stress scale
- Global Physical Activity Questionnaire (GPAQ)

Visit/Intervention Schedule 3.2

Study Visit Number	1							2								3	4	5
Study day (0-15)	0	1	2	3	4	5	6	7	8	9	10	11	12	13	14	15	16	17
Week of study	1	2						2							3			12
Decide if you want to participate	✓																	
Study training	✓																	
Study checkup								>								>	>	✓
Complete questionnaires	✓															√	✓	1
Measure body composition	✓															✓		✓
Collect stool		✓	1	✓	✓	✓	✓	✓	✓	✓	✓	✓	✓	✓	✓			✓
Record diet		✓	✓	✓	✓	✓	✓	✓	✓	✓	✓	✓	✓	✓	✓			1
Take dietary supplement		✓	√	✓	✓	√	✓	✓	✓	✓	1	✓	✓	1	✓	✓	✓	✓
Fasting blood draw	✓															✓		✓

Statistical Design and Microbiome Analysis 4

This longitudinal study will allow for the use of each subject as their own control. We will perform testing for associations between diet, taxa, groups of bacterial taxa (and their functional capacities) with metadata parameters in different combinations. We will test the null hypotheses that there are no associations between dietary intake variability and microbiome composition within and between subjects, and between dietary intervention groups. Finally, we will test the null hypothesis that vitamin D has no effect on the microbiome.

IRB # 1845028-2 Version 3 Date: March, 3 2022 **Primary Outcome:** Microbiome composition and the relationship with dietary and supplemental intake of vitamin D and serum vitamin D levels

Secondary Outcomes: Circulation inflammatory markers (e.g. TNFα, IL-8, CRP); markers of gut permeability (e.g. zonulin, intestinal fatty acid binding protein, soluble CD14, lipopolysaccharide and lipopolysaccharide-binding protein); glucose and insulin; and other nutritional and microbial metabolites.

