4.1 Sample Size

We will enroll 40 adults in this study. The adults will be randomized, with 20 individuals per study arm, to receive either vitamin D (4000 IU daily) or placebo during the intervention period. To control for initial vitamin D (25(OH) D3) levels at baseline (including those with hypovitaminosis), subjects will be randomized using 1:1 matching based on vitamin provided from blood samples at study visit 1. Study PI will be blinded to subject randomization. We will obtain 15 stool samples and 15 24-hour dietary recalls from each individual, for a total of 561 stool samples and 561 dietary records. We will obtain pre- and post- intervention blood samples from each individual for a total of 81 blood samples. We performed a power analysis using vitamin D as the primary exposure, and the top 10 dominant microbial taxa as the primary outcome. Using monte carlo simulation of microbial taxa distributed according to a lognormal distribution, and a non-parametric Mann-Whitney U test for significant differentiation, we found that this sample size is sufficient to detect a change of ≥ 1.24 standard deviations in any one of the dominant taxa. This analysis accounted for multiple hypothesis testing using Bonferroni correction.

5 Participant Selection

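### For Aim 2 no baseline-adjusted comparison of the arms is named, and a stool from before the first gummy is not assured; the cost is precision, not validity.

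*Combined protocol and SAP*

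**What the plan says.** - Section 4 states, for the study in general: "This longitudinal study will allow for the use of each subject as their own control". It then lists null hypotheses, the last being that vitamin D has no effect on the microbiome. It gives no time point and no baseline term for that test.
- Section 3.1 lists two activities for Study Days 1-14: "Consume vitamin D or placebo as gummies for 14 days" and "Collect 1 stool sample per day for 14 days". The Day 0 list contains no stool sample. In the Section 3.2 schedule, Day 0 is blank for both stool and supplement.
- Section 4.1: "We will obtain 15 stool samples and 15 24-hour dietary recalls from each individual". For blood, by contrast, it says: "We will obtain pre- and post- intervention blood samples from each individual". No stool is labelled baseline.
- Section 4.1 bases power on "a non-parametric Mann-Whitney U test for significant differentiation" and concludes that the sample size is "sufficient to detect a change of ≥ 1.24 standard deviations in any one of the dominant taxa".
- Section 6.4 (supplement) ties the gummies to the largest meal. Section 6.2 asks for one stool on each day that one is passed, and expects some days without.
- Section 2.1, under Aim 1, counts the starting microbiome among the main determinants of microbial response and says the longitudinal data will control for initial composition.

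**The concern.** Aim 2 asks which shifts in composition vitamin D causes. A shift needs a reference point, and a person's starting microbiome is likely to predict the later one. An arm comparison that ignores it leaves between-person variation in the error term, which matters with 20 per arm and ten taxa tested. The plan neither names an adjusted analysis nor secures the sample on which the cleanest adjustment would rest. A chance imbalance in a taxon could be approximated from the early stools. If those stools already reflect some treatment, however, imbalance and early effect cannot be reliably separated.

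**Working it through.** **1. Where the stools fall.** Days 1-14 give 14 stools and the closing visit gives 1: 14 + 1 = 15, the number in Section 4.1. All 15 fall on supplement days, so there is no separate slot for a pre-dose stool. A Day 1 stool may come before the first gummy, after it, or not at all. If a share p of Day 1 stools came first (p is assumed), 40p participants would have a pre-dose value: 12, 20, 28 or 36 at p = 0.3, 0.5, 0.7 or 0.9.

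**2. The plan's own figure.** Inputs from Section 4.1: 20 per arm, ten taxa, Bonferroni. Assumed because not stated: overall alpha 0.05, two-sided, so 0.05/10 = 0.005 per taxon; power 80%. At 1.24 SD a t test has 82% power. A simulated Mann-Whitney test has 77% for a shift on the log scale and 82% to 99% for a raw-scale shift (log SD 0.25 to 1). So 1.24 SD is plausible for a target near 80%, but cannot be confirmed. It compares two independent groups without a baseline. The t test reaches 80% power at 1.217 SD, used below as the unadjusted value.

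**3. One pre-dose stool as covariate.** The outcome is log abundance in the final stool, with constant within-person correlation ρ (not in the documents). Detectable difference = 1.217 × √(1 − ρ²):
- ρ = 0.3: 1.217 × 0.954 = 1.161
- ρ = 0.5: 1.217 × 0.866 = 1.054
- ρ = 0.7: 1.217 × 0.714 = 0.869

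**4. Mean of the Day 1 and Day 2 stools as covariate.** Let these stools carry a share c of the final effect. Then v = ρ + (1 − ρ)/2, slope b = ρ/v, detectable difference = 1.217 × √(1 − ρ²/v) / (1 − cb), and shrinkage of the estimate = cb. Example, ρ = 0.5 and c = 0.25: v = 0.75, b = 0.667, 1.217 × 0.8165 = 0.994, and 0.994 / 0.833 = 1.193; shrinkage 16.7%.

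| Share carried, c | Detectable SD (ρ = 0.3, 0.5, 0.7) | Shrinkage |
|---|---|---|
| 0 | 1.130, 0.994, 0.792 | none |
| 5% | 1.157, 1.028, 0.826 | 2%, 3%, 4% |
| 10% | 1.185, 1.065, 0.863 | 5%, 7%, 8% |
| 25% | 1.277, 1.193, 0.998 | 12%, 17%, 21% |

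Two averaged stools beat one pre-dose stool while c is below about 6%, 9%, 11%. Above about 16%, 28%, 42%, adjusting for them is no better than not adjusting.

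**5. Missing samples.** Simulated power at true differences of 1.161, 1.054 and 0.869 SD, with the slope estimated; figures are good to about one percentage point.

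| Analysis | Power (ρ = 0.3, 0.5, 0.7) |
|---|---|
| Unadjusted | 75%, 63%, 43% |
| Pre-dose stool, complete | 78%, 78%, 78% |
| Pre-dose stool, 20% missing, with indicator | 76%, 73%, 68% |
| Day 1-2, 20% of samples missing, c = 5% | 77%, 77%, 78% |
| Day 1-2, 20% of samples missing, c = 10% | 74%, 74%, 74% |
| Day 1-2, 20% of samples missing, c = 25% | 65%, 61%, 58% |

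At ρ = 0.3 with 20% missing, the pre-dose adjustment gains essentially nothing; at 0.5 and 0.7 it gains about 10 and 25 points over no adjustment.

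**The case against.** The strongest reply is that the missing pre-dose stool may cost nothing. The Day 1-2 stools already planned serve about as well when early response is small, and the documents do not suggest that it is large: the response within 1 to 2 days in Section 2.1 concerns altered diet, and the supplementation result in Section 2.2 is at 12 weeks. A short pre-dose window would also miss some participants. This stands. Most of the gain comes from adjusting at all, so the unnamed analysis is the main gap and stool timing is secondary.

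It can also be said that the own-control sentence is general and that the sentence on initial composition belongs to Aim 1. Both are true. Own-control works for Aim 1, where daily stools are paired with diet records, and neither sentence promises a pre-dose stool for Aim 2.

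Thirdly, nothing confines the vitamin D test to the final stool, and an analysis of arm by time over all 15 is possible. It is not named either, and the figures above do not cover it.

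A reader might infer that no pre-dose stool will exist, or that every first stool follows dosing. The documents do not say so: a Day 1 stool passed before the largest meal would be pre-dose. Nor does adjusting for early stools necessarily shrink the effect; it does so only if they carry some of it.

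**Conclusion.** The point holds as a gap in precision and specification that should be fixed. The schedule facts are clear from Sections 3.1, 3.2 and 4.1. The size of the benefit depends on a correlation and an early-response share that the documents do not give; 0.3 to 0.7 and 5% to 25% are assumed ranges. Within them, a complete pre-dose covariate lowers the detectable difference by 0.06, 0.16 or 0.35 SD (1.22 less 1.16, 1.05 or 0.87). A labelled pre-dose stool mainly removes dependence on an unknown early response.

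It might be inferred that the trial cannot test Aim 2, that the arm contrast is biased, or that 1.24 SD is too optimistic for want of a baseline. The documents do not support this. Randomization makes the 20 against 20 comparison valid without a baseline, and the power calculation never relied on one.

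**What to change.** **Main part, Section 4.** State that, for each dominant taxon, the arms are compared on log abundance with baseline log abundance as covariate, and say which follow-up stool or stools are used. Keep participants without a baseline by using the overall mean baseline and a missing-baseline indicator. Add a sensitivity analysis that excludes them. The cost is one paragraph.

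**Safeguard, Sections 3.1, 3.2 and 6.2.** Section 3 already provides that "At visit 1 participants will receive stool collection kits for week 1". Use one of these kits for a stool between Visit 1 and the first gummy, record the date and time of both, and label that stool baseline. With the total kept at 15, kits, sequencing and visits do not change. The cost is two time fields, revised instructions and one fewer on-supplement daily stool (13 instead of 14). Aim 1 also loses one diet-stool pair unless the matching recall moves too. Some participants will still lack a baseline. The version date (March 2022) is later than the stated start of recruitment (January 2022), so anyone already dosed without a confirmed pre-dose stool should be flagged as lacking one.

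**If the safeguard is not feasible,** name the earliest stools (Day 1-2) as the covariate and state the possible shrinkage.

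**To reconcile.** Section 3 hands out gummies at Visit 1, whereas Section 4.1 allocates from the Visit 1 blood result. The sponsor must reconcile the two, since the length of the pre-dose window depends on it.

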4.1 Sample Size

We will enroll 40 adults in this study. The adults will be randomized, with 20 individuals per study arm, to receive either vitamin D (4000 IU daily) or placebo during the intervention period. To control for initial vitamin D (25(OH) D3) levels at baseline (including those with hypovitaminosis), subjects will be randomized using 1:1 matching based on vitamin provided from blood samples at study visit 1. Study PI will be blinded to subject randomization. We will obtain 15 stool samples and 15 24-hour dietary recalls from each individual, for a total of 561 stool samples and 561 dietary records. We will obtain pre- and post- intervention blood samples from each individual for a total of 81 blood samples. We performed a power analysis using vitamin D as the primary exposure, and the top 10 dominant microbial taxa as the primary outcome. Using monte carlo simulation of microbial taxa distributed according to a lognormal distribution, and a non-parametric Mann-Whitney U test for significant differentiation, we found that this sample size is sufficient to detect a change of ≥ 1.24 standard deviations in any one of the dominant taxa. This analysis accounted for multiple hypothesis testing using Bonferroni correction.

5 Participant Selection

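### Bonferroni, used in the section 4.1 power analysis, is the only multiplicity method named; prespecifying Holm for the ten taxon tests would recover some power at the same family-wise error

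*Combined protocol and SAP*

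**What the plan says.** Section 4.1 (Sample Size) fixes the size and allocation: "We will enroll 40 adults in this study", and "The adults will be randomized, with 20 individuals per study arm". The power analysis takes vitamin D as the exposure and "the top 10 dominant microbial taxa as the primary outcome". Its method is described as "Using monte carlo simulation of microbial taxa distributed according to a lognormal distribution, and a non-parametric Mann-Whitney U test", and the stated result is that the sample size suffices to "detect a change of ≥ 1.24 standard deviations in any one of the dominant taxa". The closing sentence is "This analysis accounted for multiple hypothesis testing using Bonferroni correction".

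Section 4 (Statistical Design and Microbiome Analysis) describes the tests planned on the trial data: "We will perform testing for associations between diet, taxa, groups of bacterial taxa", together with a test of the null hypothesis that vitamin D does not affect the microbiome. It names no multiplicity method. Family-wise alpha, sidedness and target power are not stated in either section.

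**The concern.** Section 4.1 is the only place where the primary taxon comparison is given working detail: ten taxa, a Mann-Whitney test and a Bonferroni correction. An analyst looking for a rule for the final data would find that one and nothing else.

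Single-step Bonferroni holds every taxon to the same strict threshold, even after other taxa have been rejected. Holm starts at the same threshold and relaxes it after each rejection. It controls the family-wise error strongly under any dependence between taxa, and it rejects everything that Bonferroni rejects. The two differ only when more than one taxon truly moves. That is plausible here: Aim 2 in section 2.2 speaks of shifts in the plural, and the same section cites an earlier supplementation study in which a phylum-level ratio and two genera changed. With 20 per arm, power per taxon is limited and worth keeping.

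**Working it through.** **Inputs from section 4.1:** 20 per arm, ten taxa, Mann-Whitney U on lognormal data, detectable change 1.24 SD, Bonferroni.

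**Assumptions, because the documents are silent:** family-wise alpha 0.05 two-sided, power 80%, SD measured on the log scale.

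**Step 1. Reproduce the 1.24 SD figure.** The Bonferroni threshold per taxon is 0.05/10 = 0.005. With 20 per arm and a 1.24 SD shift, simulated Mann-Whitney power at two-sided 0.005 is:
- 79.0% with exact p-values
- 78.0% with the asymptotic test
- 77.0% with the continuity-corrected asymptotic test

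Exact power is 80.6% at 1.26 SD, so interpolation puts the 80% point at 1.24 + 0.02 × (80.0 − 79.0)/(80.6 − 79.0) ≈ 1.25 SD. As a cross-check, the noncentral t gives 1.217 SD, and 1.217/√0.955 ≈ 1.246. The stated figure therefore fits division by ten at an assumed 80% power. Without any correction, power at 1.24 SD would be 96.0%. At 90% power even a t test would need about 1.36 SD.

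This match depends on the log-scale reading. With the SD on the raw scale, power at 1.24 SD ranged from about 47% to 99% across the lognormal shapes and shift types tried.

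**Step 2. The two rules.** Order the p-values p(1) ≤ … ≤ p(10).
- Bonferroni rejects every p ≤ 0.005.
- Holm rejects p(j) as long as p(i) ≤ 0.05/(10 − i + 1) for every i up to j. The thresholds are 0.05/10 = 0.005, 0.05/9 = 0.0056, 0.05/8 = 0.0063, and so on up to 0.05/1 = 0.05.

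The first thresholds are identical, so the two rules always agree on whether anything is rejected.

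**Step 3. Compare them.** Independent taxa, 1.24 SD shifts and continuity-corrected p-values were used, with 40,000 simulated trials per scenario except for seven shifted, which comes from a separate run. The figures are average power per truly shifted taxon.

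| Taxa truly shifted (of 10) | Bonferroni | Holm | Gain (points) |
|---|---|---|---|
| 1 | 76.6% | 76.6% | under 0.1 |
| 2 | 77.2% | 78.1% | 0.9 |
| 3 | 76.8% | 78.9% | 2.1 |
| 5 | 77.0% | 81.7% | 4.7 |
| 7 | 77.2% | 85.2% | 8.0 |
| 10 | 76.9% | 92.8% | 15.9 |

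The chance of finding all five when five shift rises from 27% (check: 0.77⁵ = 0.27) to 38–39%. For a smaller shift of 1.0 SD in five taxa, average power rises from 51.4% to 55.8%.

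**Step 4. Sensitivity and error control.** With between-taxon correlation 0.3 the gains are slightly smaller: 76.9% to 81.2% with five shifted (4.3 points) and 77.1% to 90.7% with ten (13.6 points). Simulated family-wise error was at most 3.8% for either method. With five shifted and independent taxa it was 1.9% for Bonferroni and 3.7% for Holm. No Bonferroni rejection was lost under Holm, and whether at least one taxon was rejected was the same in every simulated trial.

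**The case against.** The strongest reply is that the Bonferroni sentence belongs to the sample-size simulation. A reader might infer that the plan prescribes single-step Bonferroni at 0.005 for the trial data. The documents do not say so: the sentence follows directly from the description of the power analysis, no alpha is given, and section 4 leaves the final method open. That stands. The point is therefore conditional on the final tests following the power analysis.

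A reader might also infer that true taxon shifts will be missed for no return. That goes too far. Bonferroni is valid and conservative, and it gives simple simultaneous confidence intervals, whereas those matching Holm are more complicated. Holm also spends more of the permitted error, though it stays within the same bound.

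Third, the stated target is a change in any single taxon, and for that target Holm changes nothing. This stands too. The gain needs several true shifts, and the documents give neither their number nor their sizes. The earlier study cited in section 2.2 is reported without SDs, and nothing says that its genera are among the ten dominant taxa here.

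Finally, Holm over ten taxa does not deal with the wider set of diet and metadata associations in section 4. That is a separate gap. What survives all this is that a method has to be stated for the ten taxon tests, and Holm fits the existing power basis at least as well as Bonferroni does.

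**Conclusion.** The point holds as an optional improvement. Bonferroni is the only multiplicity method named, it is attached only to the power analysis, and carrying it over unchanged to the ten final taxon tests would give up power that Holm recovers under the same family-wise bound. The gain ranges from nothing with one shifted taxon, through about 1, 2 and 5 points with two, three and five, to about 8 points with seven. These figures assume two-sided family-wise alpha of 0.05, 20 per arm and 1.24 SD shifts on the log scale; the number of shifted taxa is also an assumption. They do not show that the sample size is wrong, that the 1.24 SD claim fails, or that using Bonferroni was a mistake.

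**What to change.** Add one sentence to section 4: the ten primary taxon comparisons between arms are tested with Holm's step-down procedure at a two-sided family-wise level of 0.05. In section 4.1, keep Bonferroni as the conservative basis of the sample-size figure; nothing there needs recalculating. Make the change before the data are examined, so that the choice of correction cannot depend on the results.

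It needs no further participants, samples or assays and does not loosen the family-wise bound. The one cost is that simultaneous intervals matching Holm's decisions are less simple than Bonferroni intervals. A permutation-based step-down version is not proposed: it was not evaluated here, and it would depend on how the 1:1 matching in section 4.1 is read.
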